Months 1-6: Group weight management class: 1x/wk, 45-min led by study interventionist; Individual weight management visit: 1x/month, 15-20 min with interventionist; Group exercise classes: 3x/week, 50-min led by interventionist. PRP staff delivered video-assisted classes 1x/wk in mo. 6-12, 2x/wk in mo. 13-18.	Months 1-6: Multipurpose class: group weight management + exercise: 3x/wk, 45 to 60-min class (~20-30 min weight mgmt, ~20-30 min exercise) led by a PRP staff member and peer leader trained as ACHIEVE-D coach/peer-leader.
Weigh-ins: weekly, 2 min	Weigh-ins: weekly, 2 min
Curriculum Delivery Modality	
Weight mgmt: In-person Exercise: Staff led or video-assisted	Weight mgmt: In-person with short videos Exercise: Video-assisted
Goals and Recommendations	
Weight loss goal 10lbs in 18 mo. (tailored to indiv.)	Weight loss goal 5lbs in 6 mo. (tailored to indiv.)
Behavioral Recommendations: 6 messages	Behavioral Recommendations: 6 messages

Modifications to the curriculum delivery and schedule – e.g. video-assisted, combined exercise and weight management sessions–could help support efficient, staff-led delivery. However, whether these adaptations will produce similar behavior change results have not yet been tested. Based on their experience conducting the ACHIEVE trial, the study team is making these modifications to adapt the ACHIEVE intervention into the ACHIEVE-Dissemination or “ACHIEVE-D” curriculum for community mental health settings. The curriculum adaptations are described in more detail below:

(1) **Class Format:** Group weight management and exercise will be combined into one multi-purpose class in ACHIEVE-D. To increase efficiency of delivery, ACHIEVE-D will be conducted in group sessions only; in lieu of the individual weight management sessions used in ACHIEVE, coaches and peers will be encouraged to set individualized behavioral goals related to the topic of the week during the discussion portion of group sessions.

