In this study, we will pilot test two months of the ACHIEVE-D curriculum in a community-based psychiatric rehabilitation program (PRP) to determine whether this format is acceptable to participating PRP consumers. The study team has prior experience collecting qualitative and quantitative data and delivering interventions among persons with SMI and has a long-term relationship with the study site (Prologue, Inc.) where this research will be conducted.

4. Study Procedures

a. Study design

We will conduct a pre/post study of two months (8 weeks) of the ACHIEVE-D curriculum. We will conduct a focus group among mental health consumers, as well as secondarily compare their outcomes pre- and post- intervention. The study will invite PRP staff as well as peer leaders to observe all the sessions during this pilot. We will conduct a focus group among PRP staff and peer leaders who observe the intervention sessions. Our primary outcomes will be to determine the acceptability and feasibility of the adapted curriculum.

Description of ACHIEVE-D Intervention

We will test two modules of the adapted video-assisted curriculum format (Tables 1 & 2).

Consumers will participate in 45 to 60-minute multipurpose classes three times per week, which will include a segment on group weight management (~20-30 minutes) and group exercise (~20-30 minutes). Within each module, the group weight management topic varies by week, and within each week the content of the three weight management groups builds gradually and is purposely repeated. Within each module, the group exercise classes will focus on mild to moderate intensity aerobic exercise using an exercise video. The class will have a progression of

intensity and duration appropriate for sedentary individuals. Classes will start at a lower intensity for 10-15 minutes and gradually progress to moderate intensity aerobic exercise for 20-30 minutes per session across the two-month period. Participants will also be encouraged to engage in moderate intensity exercise, such as brisk walking, of similar duration on days when they are not at the PRP. In this pilot study, a trained study interventionist will deliver the ACHIEVE-D curriculum, as our aim is to determine acceptability of this new format with consumers, PRP staff and peer leaders prior to training the PRP staff and peer leaders to deliver the content, which is planned for a subsequent study.

Procedures related to Hypothesis 1 – Consumers with SMI

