Recruitment. We will recruit participants from Prologue, which is a PRP based in Baltimore with whom the study team has a long-term relationship (see letter of support). We will use similar methods as in prior and ongoing studies. We will recruit consumers with SMI who are willing to participate and have no contraindications to participating in a diet and physical activity program (see eligibility criteria described in following section).

We will make presentations during regular consumer meetings at the PRP where we will provide information about the study. We will also display recruitment flyers in the PRP (Flyer). We will use a telephone script to handle all calls or in-person inquiries generated from these presentations and flyers (Screening Script). Consumers who are interested in participating will sign up to attend a consent/screening visit. To address privacy issues during recruitment, all participants who are contacted or who approach us for recruitment will be assured that the research staff at Johns Hopkins will be the only ones to see their information, and that the information we collected will be kept private and be used only for the research study we are discussing. If the potential participant chooses not to enroll in the study or does not qualify to be in the study, then his/her information will be destroyed.

Consent & Screening. We plan to screen a total of 20 consumers with the goal of enrolling approximately 10 into the study. Participant eligibility will be determined at the consent/screening interview (Table 3).

Consent

The study will be explained in detail to the potential participants in a one-on-one format onsite at the PRP in a private room. Informed consent for the study will be obtained from each eligible participant at the beginning of this visit (Consumer Written Consent). In particular, consumers will be advised of the voluntary and confidential nature of participation. Consumers will be asked questions about the study procedures to test their understanding. They will also be provided the contact information of the principal investigator. We will emphasize that their participation in the study will not affect their care at the PRP or Johns Hopkins. After consent is obtained, then potential participants will be screened.

Screening

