The consumer will meet individually with a research staff member onsite at the PRP in a private room. Basic demographics will be assessed. A brief medical history will be taken and the 2018 Physical Activity Readiness Questionnaire+ (2018 PAR-Q+) will be administered as part of the exercise pre-participation health screening. Consumers will give permission for their primary care physicians to be contacted regarding medical eligibility for participation in moderate exercise and for review of Prologue on-site medical records. We will assess for alcohol and illicit substance use. Height and weight will be measured using standard procedures. We will

Date: May 15, 2019

Principal Investigator: [name]

Application Number: IRB00194122

measure weight to the nearest 0.1 lb by a high quality digital scale with participants wearing light indoor clothes without shoes. Weight will be measured in lbs for ease of interpretation by participants and converted to kg for calculation of BMI. The scale will be calibrated quarterly using standard weights by trained study personnel. Height, without shoes, is measured once at baseline using a wall-mounted stadiometer. Body mass index is calculated as the Quetelet index (kg/m^2). Consumers who meet all eligibility criteria (see eligibility criteria described in following section) will be enrolled into the pilot study.

Primary Outcome – Consumer Focus Group Procedures. At the end of the preliminary pilot period, we will conduct one 90-minute focus group with consumers. The focus group will assess consumers' satisfaction, perceptions and attitudes regarding the ACHIEVE-D program. We will inquire with them regarding their satisfaction with the curriculum, including seeking feedback on feasibility of format, understandability of content, and likability of intervention materials, as well as challenges/issues that they experienced. We will also discuss whether members were successful in making diet and physical activity changes, as well as barriers and facilitators to making the change. This focus group will be held in a private room in the PRP. We will use a moderator guide for the focus group (Consumer Focus Group Moderator Guide). The group will be tape-recorded and conducted by a moderator. The focus groups will be transcribed by Production Transcripts.

Secondary & Other Outcomes – Survey, Anthropometric and Process Measure

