Procedures. This data will be collected during study visits at baseline and follow-up for enrolled participants held onsite at the PRP in a private room. Surveys will be administered in-person by trained research assistants. All data will be collected on Johns Hopkins encrypted, password protected laptop computers and entered into a RedCap database. Because of consumers' generally low literacy and problems with cognition, all instruments will be interviewer administered to decrease the burden on participants and improve validity of data collection. Enrolled participants will complete baseline data collection measures (Table 3).

During the intervention, we will also collect data on participants regarding attendance, weight from weigh-ins during the sessions, hours per week each consumer participated in ACHIEVE-D exercise classes, as well as diet and physical activity via weekly self-reported logs.

We will video record each class session (3 classes per week for 8 weeks – 24 sessions total) and grade the sessions using a fidelity tool (ACHIEVE-D Fidelity Tool), which measures to what extent the coach implements the core components of ACHIEVE-D and uses a motivational interviewing delivery style. Once videos are evaluated for fidelity, any that are not needed will be destroyed; some will be stored on a Johns Hopkins secure network drive and used for future training in fidelity monitoring. In addition, short video clips from these sessions may be incorporated into materials for the larger R34 study including to train coaches.

After completion of the intervention, consumers will complete a survey including asking questions regarding satisfaction with the curriculum, self-reported sugar sweetened beverages and sedentary behaviors, and anthropometric measurements will be repeated at this time. We will also repeat other measures as described in Table 3.

Table 3. Data Collection Schedule

	Consent/ Screening	Baseline	Follow-up	
			During	Post
Informed consent	x			
Demographics	x			
Medical history	x			x
Medications	x			
Substance use (ASI-Lite)	x			
Exercise pre-participation screening (2018 PAR-Q+)	x			
Weight	x	x	x	x
Height	x			x
Primary Outcomes				
Consumer focus group				x
PRP staff & peer leader focus group				x
Secondary Outcomes				
Diet				
EARLY Eating Away from Home Q		x		x
EARLY SSB Consumption Q		x		x
Physical Activity				
CARDIA/EARLY Q – sedentary behavior		x		x
Eating Behaviors				
Palatable Eating Motives Scale (PEMS) – Coping Subscale		x		x

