Trait Food Craving Q – Reduced Form		x		x
Reward-based Eating Drive (RED) Scale		x		x
Psychological & Support				
Perceived Stress Scale (PSS)		x		x
Important Others' Q		x		x
Anthropometric Measurements				
Waist circumference		x		x
Process Measures				
Consumer attendance & exercise at group sessions			x	
Consumer food and physical activity logs			x	
Consumer Satisfaction Q - Nabati				x
Coach Fidelity to ACHIEVE-D			x	

Abbreviations: SSB – sugar-sweetened beverage; Q – questionnaire

Below we describe the planned secondary outcomes:

Acceptability

A 12-item Consumer Satisfaction Questionnaire based on the instrument developed by Nabati and colleagues will be used to determine acceptability. Following the intervention, in addition to the focus group, we will use this standard measure of satisfaction with the intervention. We will also examine participation as a reflection of acceptability. Participation in intervention sessions will be measured by attendance at the group classes, the number of sessions attended, and proportion attending at least 80% of sessions.

Date: May 15, 2019

Principal Investigator: [name]

Application Number: IRB00194122

Diet

We will administer the EARLY Sugar-Sweetened Beverage (SSB) questionnaire at baseline and post-intervention, which has been selected by the NIH as Accumulating Data to Optimally Predict Obesity Treatment (ADOPT) Core Measures for diet.

Physical Activity

We will administer the sedentary behavior inventory from CARDIA/EARLY at baseline and post-intervention, which has been selected by the NIH as ADOPT Core Measures for self-reported physical activity.

Weight & Waist Circumference

Weight will be measured at baseline and post-intervention using standard procedures as described in the screening section above. Waist circumference is measured using a tape, according to a standardized protocol at baseline and post-intervention.

Below we describe the other planned survey measures in this study:

Demographics

Most demographic data will be obtained from Prologue's intake assessment, but we will obtain updated marital status and living arrangements as well as confirm educational level. This data will be collected at the screening visit.

Medical History

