We will conduct descriptive analyses of baseline data. Our acceptability outcomes among consumers will include their satisfaction with the intervention as well as program attendance. Our behavior change outcomes among consumers will include changes in dietary and physical activity measures pre-post. We will examine changes in diet and physical activity outcomes with t-tests and Chi Square tests, as appropriate. If these outcomes are not normally distributed, then we will use Wilcoxon signed-rank tests in lieu of t-tests.

c. Statistical plan including sample size justification and interim data analysis.
Not applicable to qualitative data collection

d. Early stopping rules.
Not applicable

8. Risks

a. Medical risks, listing all procedures, their major and minor risks and expected frequency.

ACHIEVE-D Intervention Risks.

The 2 month behavioral weight loss intervention sessions should be minimal risk for participants. Physical activity may pose a small risk of musculoskeletal injury. In addition, making dietary changes and engaging in moderate-intensity exercise may also pose risks such as needing to adjust the dose of certain medications (e.g., hypoglycemic agents) or may be inappropriate for people with certain medical conditions.

Focus Group Risks. This study involves focus group discussion. Every effort will be made to protect confidentiality. There is minimal risk to the participant. If a participant changes her/his mind and does not wish to complete the focus group discussion, s/he will be allowed to leave.

Data Collection Risks. Risks related to the data collection include loss of confidentiality, and potential discomfort, boredom or inconvenience from participating in a focus group and answering survey questions and undergoing anthropometric measurements.

b. Steps taken to minimize the risks.

Minimizing ACHIEVE-D Intervention Risks.

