Minimizing Data Collection Risks. There is a risk of the loss of confidentiality of medical information. We will ensure protection of the data and any personal health information. Only the study team will have access to participant's identifying information. Each participant will be assigned an identification (ID) number at the time of recruitment. The database that links the ID with the participant will only be accessible by the principal investigator and core investigative team. Data will be stored in RedCap and when exported on a Hopkins (JHMCIS managed) network drive which is password-protected and backed-up each night. If a participant changes her/his mind and does not wish to complete the study s/he may withdraw at any point.

Participants will be aware through the consent process that videos will be taken of the group sessions and that clips may be incorporated into future training materials or posted on [name] research website.

There is a risk of potential stress, discomfort, boredom or inconvenience from answering survey questions and undergoing anthropometric measurements. Participants will be informed that they do not have to answer any questions that they do not wish or have their waist circumference, height, or weight measured. There are risks related to interview location at the PRP. To ensure participants' privacy, we will conduct interviews in a private space.

c. Plan for reporting unanticipated problems or study deviations.

Unanticipated problems or study deviations will be reported to the IRB, the NIH, and if applicable to all study participants in a letter.

d. Legal risks such as the risks that would be associated with breach of confidentiality.

None

e. Financial risks to the participants.

None

9. Benefits

Consumers may benefit from participating to increase their knowledge about healthy diet and physical activity. This study may provide benefit to society at-large, as our results will help us determine whether the ACHIEVE-D curriculum is acceptable to consumers with SMI. We believe that the risks to subjects are minimal and reasonable given the knowledge to be gained. There are no direct benefits to the PRP staff or peer leaders; however, their input is likely to improve the design and implementation of the ACHIEVE-D curriculum in a future trial.

Date: May 15, 2019

Principal Investigator: [name]

Application Number: IRB00194122

10. Payment and Remuneration

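### Do weight and waist need a new analysis, with a mixed model for the weekly class weights, because section 7b names no method for them?

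*Combined protocol and SAP*

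**What the plan says.** Section 4, in the list of planned secondary outcomes, has an entry for weight and waist circumference. For weight it states: "Weight will be measured at baseline and post-intervention using standard procedures as described in the screening section above". Waist is taken at the same two times. The weighing procedure is given under Screening: staff will "measure weight to the nearest 0.1 lb by a high quality digital scale with participants wearing light indoor clothes without shoes". Table 3 puts waist under Secondary Outcomes and shows weight at screening, baseline, during and post, in a row above the outcome headings. The status of weight as an outcome therefore rests on the text of section 4.

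Section 4a says the study will hold a consumer focus group "as well as secondarily compare their outcomes pre- and post- intervention". Section 7b then covers baseline description, satisfaction, attendance, and this: "Our behavior change outcomes among consumers will include changes in dietary and physical activity measures pre-post". Its t-tests, chi-square tests and signed-rank fallback are attached to diet and physical activity. Section 7c gives no quantitative plan.

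The weekly weights appear twice. Table 1 lists them as an intervention contact ("Weigh-ins: weekly, 2 min"), and section 4 says "we will also collect data on participants regarding attendance, weight from weigh-ins during the sessions". No analysis is attached to them. Section 8b tells participants that "they do not have to answer any questions that they do not wish or have their waist circumference, height, or weight measured". Planned size: "We plan to screen a total of 20 consumers with the goal of enrolling approximately 10 into the study".

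**The concern.** Two secondary outcomes have no named method, in a trial of a weight-loss curriculum whose entrants must want to lose weight. A weight change will probably be reported, and choosing the method after seeing the data is normally a fault.

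Missing data sharpen the worry. Participants may refuse weighing or withdraw, and no rule covers a missing weight. With about 10 consumers, each missing post weight removes about a tenth of a paired analysis. If those who leave differ in weight change from those who stay, the paired mean is biased. Up to eight weekly weights per person could carry information about those who leave, and the plan does not say it will use them.

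The apparent remedy is a mixed model on all weights, with a random intercept and slope and a class-versus-visit term. The term is there because nothing says class weigh-ins follow the light-clothing, no-shoes procedure.

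**Working it through.** **1. What is settled and what is open.** Section 4 names the outcomes, their two time points and how visit weights are taken. Section 4a says outcomes are compared before and after. The same people are measured twice, so the comparison is paired. Only the test or interval and the handling of missing values are left open. Section 7b already uses t-tests with a signed-rank fallback for change outcomes, and extending these to weight and waist is the obvious reading.

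**2. Inputs.** From the documents: n of about 10; a weight goal of 5 lb in 6 months (Table 1), pro-rated to 2 months as 5 × 2/6 = 1.67 lb. Assumed, because the documents give no figures: between-person SD of true 8-week change 5 lb (range 3 to 8), noise of a single weighing 2 lb (range 1 to 3), class weights 2 lb heavier than visit weights, 70% of weigh-ins attended. The plan states no figure to reproduce.

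**3. Precision of the paired change.** SE = √[(SD² + 2 × noise²)/n].
- n = 10: √[(25 + 8)/10] = 1.82 lb; 95% half-width 2.262 × 1.82 = 4.1 lb.
- n = 7: √(33/7) = 2.17 lb; half-width 2.447 × 2.17 = 5.3 lb.

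Either half-width is more than twice the pro-rated goal of 1.67 lb.

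**4. Gain from the mixed model with every post weight present.** SE from generalized least squares, n = 10:

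| SD of change, noise (lb) | Paired | Mixed with class term | Reduction |
|---|---|---|---|
| 3, 1 | 1.05 | 1.00 | 5% |
| 3, 3 | 1.64 | 1.32 | 20% |
| 5, 2 | 1.82 | 1.69 | 7% |
| 8, 1 | 2.57 | 2.55 | 1% |

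Simulation at (5, 2) gave 1.86 against 1.75 lb: 1 - 1.75/1.86 = 6%.

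**5. Gain with post weights missing.** Three of ten missing, all their weights lost after week 4, true change -1.67 lb:

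| Who is missing | Paired (lb) | Mixed (lb) |
|---|---|---|
| At random | -1.7 (SD 2.12) | -1.7 (SD 1.85) |
| Weakly related to early change | -2.2 or -1.1 | -1.6 or -1.7 |
| Exactly the three losing least by week 4 | -3.7 | -1.8 |
| Exactly the three losing most by week 4 | +0.2 | -1.7 |

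The last two rows are built extremes. Dropout is ranked on observed class weights, which is the condition under which the mixed model is valid. With weakly related dropout the paired bias is 2.2 - 1.67 = 0.5 or 1.67 - 1.1 = 0.6 lb, against a half-width of about 5 lb. If dropout depends on change that was never observed, both are biased: mixed -2.8 or -0.6, paired -4.0 or +0.6.

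**6. What the mixed model can lose.** Let the class-versus-visit difference drift from 0 to 2 lb over the eight weeks, with nobody missing. The simulated mixed estimate is -0.66 lb, a bias of 1.67 - 0.66 = 1.01 lb, and its root mean square error is √(1.01² + 1.75²) = 2.02 lb. The paired estimate uses visit weights only and stays at -1.70 lb, with root mean square error 1.85 lb. In this case the simpler analysis is the better one.

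**7. What identifies the class term.** Visit weights fall only before and after the class weeks. With a separate level for each of the ten occasions, the design has 11 columns and rank 10, because the class indicator is the sum of the eight class-week indicators. With linear time it has 3 columns and rank 3. The offset is thus separated from true weight change only by assuming a smooth time trend, which about 10 people can hardly check.

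**The case for a change.** The best case for a change is that the outcomes are listed, the method is not, and the remedy costs a few lines and no new data. Section 4a names neither an outcome nor an estimator. The weekly weights are the only data that could help if post weights are missing. The proposal can also be hedged: report the paired change alongside, use small-sample degrees of freedom, and fall back on the paired change if the model fails.

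Part of this stands. Section 7b does omit weight and waist, and the mixed model does protect against dropout related to weights already observed. In the two extreme scenarios, 95% interval coverage for the paired analysis fell to 79.5% and 82%, against 93% and 95.5% for the mixed model.

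The rest does not carry. Dropout at that level is assumed, and the documents point the other way: consumers must expect to stay in the program at least 6 months, and the follow-up assessment is on site and paid. Section 4 defines outcome weight at baseline and post only. Class weigh-ins are an intervention contact, collected beside attendance and activity logs, so leaving them unmodelled is not an omitted outcome analysis. They do nothing for waist, which is measured twice. A fallback to the paired change covers failed fits but not drift in the class weights, which leaves no sign in convergence.

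**Conclusion.** The gap in wording is real and minor, and it calls for no change. Outcome, timing, measurement and paired structure can all be read from section 4. What remains is the mean change, its interval and the number with both measurements, which any analyst would supply. Adding weight and waist to the sentence in 7b would be tidy, but would not alter what is done.

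The mixed model is the only part that would alter the analysis, and it is a fair trade-off to leave it out. With full follow-up the SE falls by 1% to 20% across the assumed SDs shown, and by about 6% in the central case. With three of ten missing at random the estimator SD falls by 1 - 1.85/2.12 = 13%. Against that stand a bias of about 1 lb if class weights drift by 2 lb, and a class term that depends on an assumed time shape. An analyst worried by missing post weights could still run the model as a sensitivity analysis, since the weights are collected anyway.

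The stakes are low. The primary outcomes come from focus groups, section 7a bases changes to the curriculum on their transcripts, and an interval of about ±4 to 5 lb makes the weight result descriptive under either method. These sizes rest on assumed SDs, attendance and offsets. Heavy dropout clearly related to early weight change would strengthen the case for the model, but the documents give no reason to expect it.
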